6.10 TISSUE IMMUNOGENICITY ASSESSMENT

If there is residual tissue or additional slides in the paraffin block after histologic diagnoses have been rendered, then unstained slides and/or the relevant paraffin blocks may be collected for immunohistochemistry (IHC). Assessment of markers may include, but are not limited to, CD8⁺ and FoxP3⁺ infiltrating cells as well as assessment of cell death via Cleaved Caspase 3 assessment. Additional assessments may include visualization of Granulysin, Perforin, CD137, CD103 and PD-L1 in cervical tissue as sample allows. Markers listed here may change as new relevant information becomes available.

6.11 HLA TYPING

HLA testing will be performed on PBMC from any single blood sample collected for immunogenicity analysis. If the subject has a record of previous high resolution HLA testing and access to the results, then HLA testing is not required.

The DNA extracted from the blood sample will be used to determine if alleles at the MHC locus affect the immune response to study treatment. Data arising from this analysis will be subject to the same confidentiality restrictions as the rest of the study. This specimens will be destroyed after the analysis is completed.

6.12 PAP SMEARS AND HPV TESTING

Pap smears will be obtained using ThinPrep[™] test kits at the screening, Day 0, Weeks 8, 15, 28, 36, 62, 88 and read in a central laboratory. HPV PCR by cobas[™] HPV test will be performed on the ThinPrep[™] specimen. At each of these visits, menstrual cycle status & recent history will be collected via self-report. If the Pap smear result suggests progression to cancer at Day 0, Weeks 15, 28 or 36, the investigator may schedule an ad hoc visit to perform a colposcopy and possible biopsy if clinically indicated.

The subject will be requested to abstain from any sexual activity and refrain from use of douching or vaginal lubricants/medication for a period of 24 hours prior to collection of ThinPrepTM samples to eliminate potential interference with the results of HPV testing.

At visits (i.e. Screening, Day 0, and Weeks 15, 28, 36 and 88) where multiple cervical samples are collected, the two Digene cervical swab will be collected prior to the ThinPrepTM sample. Immunology testing may be performed from digene swab.

Details of sample collection and shipment information will be provided in laboratory manual.

Additionally, if there is residual tissue available from cervical tissue from screening and Week 36 after the histologic diagnosis have been rendered, then unstained slides and/or paraffin blocks may be collected to test for HPV typing.

Also, non-cervical swabs (i.e. oropharyngeal rinse, vaginal brush and intra-anal swabs) will be collected at specified visits for HPV typing.

6.13 COLPOSCOPY AND CERVICAL BIOPSIES

Colposcopy at screening must be adequate, defined as full visualization of the squamo-columnar junction (Type I or II transformation zone) and complete visualization of the upper limit of aceto-white epithelium or suspected dysplasia. An ECC is not required for study entry. However, if an ECC was done as part of routine care during the screening period, and found to have evidence of cervical HSIL such subject should not be enrolled in the study. Colposcopy is not required to be performed at screening if adequate colposcopy was previously obtained upon collection of initial biopsy. All colposcopies performed after informed consent should be conducted according to the guidelines outlined in Appendix B.

Interval colposcopies will be performed at Day 0, Weeks 15, 28, 36, 62, and 88. An unscheduled colposcopy may be performed at the discretion of the investigator if there is suspicion of disease worsening or progression.

Digital photographs of the cervix will be captured after application of acetic acid at each colposcopic examination to document the clinical findings. If a biopsy or surgical excision is performed, images of the cervix should be collected before and after the procedure. Each site will be instructed on 1) the technique for capturing the proper images using a standard approach and 2) the process for uploading the images to a secure server. Additionally, if a vaginal or vulvar lesion should develop after a subject is enrolled, photographs should also be taken to document the clinical exam finding.

6.13.1 ECTOCERVICAL BIOPSIES

Ectocervical biopsies are required at screening to confirm eligibility. If the criteria outlined in Table 5 or 6 are met, ectocervical biopsies may also be performed at Week 36 to provide tissue for histopathologic assessment of disease regression.

Visualization of a normal appearing cervix by colposcopy is insufficient evidence to confirm disease regression at Week 36. Biopsy must be performed at the location of the screening biopsy if no disease is visible at Week 36.

Biopsies should not be performed at any other visit unless there is suspicion of disease progression. Removal of additional tissue by biopsy before Week 36 will bias results toward improvement regardless of whether the subject is in the active or placebo group. The bias introduced will obviously be more significant for smaller lesions. For this reason, if biopsies are obtained prior to Week 36, the subject will be classified as a non-regressor in the efficacy

analyses. Subject safety is paramount in this study. Therefore, if at any time the investigator may suspect disease progression and the standard of medical care would be to perform an unscheduled biopsy prior to Week 36, then his or her medical judgment should prevail over the default "Schedule of Events", Table 1.

6.13.2 UNSCHEDULED BIOPSIES

In the event an unscheduled biopsy is performed prior to Week 36, the subject will be classified as a non-responder. The subject will discontinue further study treatment and continue in the study for safety follow-up visits. The subject will be managed according to standard of care and the Investigator's judgement based on the results of the histological diagnosis from the unscheduled biopsy Additional instructions for collecting ectocervical biopsies are detailed in Appendix B. All biopsy samples/excised tissue will be sent to the central pathology lab for review by PAC.

6.14 CONCOMITANT MEDICATIONS/TREATMENTS

All medications (prescription and nonprescription) taken within 8 weeks prior to the screening biopsy date of eligible subjects must be recorded on the CRF. Actual or estimated start and stop dates must be provided. Medical procedures performed within 8 weeks prior to screening biopsy date of eligible subjects that do not affect subject's eligibility for participation and during the study (including over the counter or herbal), will be recorded on the CRFs. This information will be obtained from the subject and abstracted from any available medical records. The indication for the medication, dose, and dose regimen will be documented. Medication that is considered necessary for the subject's safety and well-being may be given at the discretion of the Investigator and recorded in the appropriate sections of the CRF.

6.15 RESTRICTIONS

6.15.1 PROHIBITED CONCOMITANT MEDICATIONS AND TREATMENTS

The following medications and treatments are prohibited:

- Long term use (≥ 7 days) of oral or parenteral glucocorticoids at a dose of ≥20 mg/day of prednisone equivalent; use of inhaled otic and ophthalmic corticosteroids are allowed
- Disease modifying doses of anti-rheumatic drugs (e.g., azathioprine, cyclophosphamide, cyclosporine, methotrexate), and biologic disease modifying drugs such as TNF-α inhibitors (e.g. infliximab, adalimumab or etanercept) at screening and throughout the study
- Administration of any non-study related, non-live vaccine within 2 weeks of any study treatment or within 4 weeks of any study treatment for any non-study, live vaccine
- Blood thinners (e.g. anticoagulants, antiplatelet drugs) or other medication that affects blood clotting within 2 to 14 days (e.g., 4-5 drug half-lives) of any study treatment, biopsy or excisional procedure (e.g. LEEP)

6.15.2 OTHER RESTRICTIONS

Subjects should not use alcohol or drugs that would interfere with study requirements during the course of the study and should report ALL medications/drugs taken to the investigator and/or other study personnel.

Subjects should refrain from becoming pregnant until 6 months following the last dose of investigational product by using appropriate contraceptive measures as (See Inclusion Criteria, Section 4.1). Lapses in contraceptive use should be reported to investigator and/or other study personnel.

Subject should abstain from sexual activity and refrain from use of douching or vaginal lubricants/medication for a period of 24 hours prior to collection of ThinPrep[™] samples.

7 EVALUATION OF SAFETY AND MANAGEMENT OF TOXICITY

7.1 SAFETY PARAMETERS

7.1.1 ADVERSE EVENTS

An adverse event (AE) is defined as any unfavorable and unintended change in the structure, function, or chemistry of the body, or worsening of a pre-existing condition, temporally associated with the use of a product whether or not considered related to the use of the product. In this study, such changes will be monitored, classified, and summarized, as Clinical or Laboratory AEs. Medical condition/diseases present before starting the investigational drug will be considered adverse events only if they worsen after starting study treatment. Throughout the course of the study, all solicited and unsolicited AEs will be monitored and reported on an AE CRF, including the event's seriousness, severity, action taken, and relationship to investigational product(s). AEs should be followed until resolution or stable and the outcome will be documented on the appropriate CRF. All AEs should be recorded in standard medical terminology rather than the subject's own words.

AEs include the following:

- Pre- or post-treatment complications that occur as a result of protocol mandated procedure during or after screening (before the administration of study drug).
- Any pre-existing condition that increases in severity, or changes in nature during or as a consequence of the study drug phase of a human clinical trial, will also be considered an AE.
- Complications of pregnancy (e.g., spontaneous abortion, miscarriage, ectopic pregnancy, fetal death, still birth, congenital anomaly of the fetus/newborn); see Section 7.1.9 for additional information on pregnancy reporting.
- AEs that occur from the study screening visit onwards and throughout the duration of the study, including the follow-up off study drug period will be recorded as an AE.
- Conditions that lead to a medical or surgical procedure.

AEs do not include the following:

- Medical or surgical procedures (e.g., surgery, endoscopy, tooth extraction, transfusion) performed as a result of an AE.
- Pre-existing diseases or conditions or laboratory abnormalities present or detected before the screening visit that do not worsen.
- Situations where an untoward medical occurrence has not occurred (e.g., hospitalization for elective surgery, social and/or convenience admissions).
- Overdose without clinical sequelae.

- Any medical condition or clinically significant laboratory abnormality with an onset date before the informed consent form is signed is not an AE. It is considered to be pre-existing and will be documented on the medical history CRF.
- Uncomplicated pregnancy.
- An induced elective abortion to terminate a pregnancy without medical reason.

7.1.2 SERIOUS ADVERSE EVENTS

A serious adverse event (SAE) is any AE that meets one of the following conditions:

- Death during the period of surveillance defined by the protocol;
- Is immediately life-threatening (e.g., subject was, in the view of the Investigator, at immediate risk of death from the event as it occurred). This does not include an AE that, had it occurred in a more serious form, might have caused death;
- An event requiring inpatient hospitalization or prolongation of existing hospitalization during the period of protocol defined surveillance (including any overnight stay in the hospital, regardless of the length of stay, even if the hospitalization is only a precautionary measure to allow continued observation). However, hospitalization (including hospitalization for an elective procedure) for a pre-existing condition that has not worsened, does not constitute an SAE:
- Results in persistent or significant disability/incapacity or substantial disruption of the ability to conduct normal life functions;
- Results in congenital anomaly or birth defect;
- An important medical event that may not result in death, be life threatening, or require hospitalization, but based upon appropriate medical judgment, may jeopardize the subject and may require medical or surgical intervention to prevent one of the outcomes listed above. Examples of such medical events include 1) allergic bronchospasm requiring intensive treatment in an emergency room or at home, 2) blood dyscrasias or convulsions that do not result in inpatient hospitalization, 3) the development of drug dependency or drug abuse or 4) the development of a malignancy;
- Is medically significant or requires intervention to prevent one or other of the outcomes listed above.

7.1.2.1 Clarification of Serious Adverse Events

- Death is an outcome of an AE, and not an adverse event in itself.
- The subject may not have been on investigational medicinal product at the occurrence of the event.
- Dosing may have been given as treatment cycles or interrupted temporarily before the onset of the SAE, but may have contributed to the event.
- "Life-threatening" means that the subject was at immediate risk of death from the event as it occurred. This does not include an event that might have led to death if it had occurred with greater severity.
- Complications that occur during hospitalizations are AEs. If a complication prolongs the hospitalization, it is an SAE.

• Inpatient hospitalization means that the subject has been formally admitted to a hospital for medical reasons, for any length of time. This may or may not be overnight. It does not include presentation and care within an emergency department nor does it include full day or overnight stays in observation status.

The investigator will attempt to establish a diagnosis of the event on the basis of signs, symptoms, and/or other clinical information. In such cases, the diagnosis will be documented as the AE and/or SAE and not the individual signs/symptoms.

Serious adverse events that are ongoing should be followed until resolution or are clinically stable. The reporting period for SAEs is described in Section 9.5.

7.1.2.2 Event Reporting for Disease Progression or Exclusionary Histologic Findings Post-study Treatment

After starting study treatment, if there is histologic confirmation of progression of cervical HSIL to micro invasive or invasive squamous cell carcinoma, the event must be reported as an SAE. Post-study treatment histologic diagnosis of adenocarcinoma-in-situ or adenocarcinoma should also be reported as an SAE. In both instances, the condition for SAE reporting should be categorized as a medically important event unless another criterion is met.

7.1.3 UNEXPECTED ADVERSE DRUG REACTIONS AND EXPEDITED REPORTING

An adverse drug reaction (ADR) is any noxious and unintended responses to a medicinal product related to any dose, for which a causal relationship between a medicinal product and an adverse event is at least a reasonable possibility; i.e., there is evidence to suggest a causal relationship between the product and the adverse event. An unexpected ADR is one, the nature or severity of which is not consistent with the applicable product information (investigator's brochure, protocol, and user manual). Reports that add significant information on specificity or severity of a known, already documented SAE constitute unexpected events. For example, an event more specific or more severe than described in the Investigator's Brochure or protocol would be considered "unexpected." Specific examples would be (a) acute renal failure as a labeled ADR with a subsequent new report of interstitial nephritis and (b) hepatitis with a first report of fulminant hepatitis.

The Sponsor will assess each serious ADR report for expectedness, to determine if it is a serious unexpected suspected adverse reaction (SUSAR) which requires prompt reporting to regulatory authorities and participating investigators as an expedited report, according to the applicable regulatory requirements. Additional occurrences of the SUSAR will be required to be reported on an expedited basis until the applicable product information is amended.

In addition to single-case reports of SUSARs, the Sponsor shall notify regulatory authorities and participating investigators of information that might materially influence the benefit-risk assessment of a medicinal product, sufficient to consider changes in product administration or overall conduct of a clinical investigation. Examples of such information include a clinically important increase in the rate of occurrence of a serious expected adverse event, the identification

of a significant hazard to the subject population, or a major safety finding from a study conducted in animals.

7.1.4 UNANTICIPATED (SERIOUS) ADVERSE DEVICE EFFECT (UADE)

Unanticipated adverse device effect means any serious adverse effect on health or safety or any life-threatening problem or death caused by, or associated with, a device, if that effect, problem, or death was not previously identified in nature, severity, or degree of incidence in the investigational plan or application (including a supplementary plan or application), or any other unanticipated serious problem associated with a device that relates to the rights, safety, or welfare of subjects.

Per the definition above, a UADE is a type of serious adverse event (SAE) that requires expedited reporting on the part of the sponsor. As a reminder, all SAEs regardless of relationship to device, drug or procedure are to be reported to Sponsor by the study investigator within 24 hours. Sponsor will assess each device related SAE to determine if anticipated based on prior identification within the investigational plan.

For countries recognizing and regulating CE Mark devices, SAEs related only to the device which meet the medical device vigilance (MDV) reporting criteria will be handled by the Sponsor under the post-market surveillance/vigilance reporting requirements per MEDDEV 2.12-1. In such cases, the Sponsor will report as per the regulations to the relevant health authorities that require MDV reporting.

7.1.5 ASSESSING SEVERITY (INTENSITY)

Adverse events should be captured once on the CRF at the maximum severity reported.

The investigator will grade laboratory AEs and clinical AEs with respect to the following levels of severity as per Common Toxicity Criteria for Adverse Events (CTCAE) v 4.03 for applicable subject populations:

- Mild (Grade 1)
- Moderate (Grade 2)
- Severe (Grade 3)
- Potentially Life Threatening (Grade 4)

The investigator will grade injection site reactions in accordance with September 2007 FDA Guidance for Industry—Toxicity Grading Scale for Healthy Adult and Adolescent Volunteers Enrolled in Preventive Vaccine Clinical Trials.

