8.11 SAFETY ANALYSES

8.11.1 ADVERSE EVENTS

All AEs will be summarized among the safety population by frequency per treatment arm. These frequencies will be presented overall and separately by dose, and will depict overall, by system

b the histopathologic efficacy time frame is defined by those who have undergone a biopsy or surgical excision at any time starting from 14 days prior to the protocol-specified target date of Week 36

organ class and by preferred term, the percentage of subjects affected. Additional frequencies will be presented with respect to maximum severity and to strongest relationship to Study Treatment. Multiple occurrences of the same AE will be counted only once following a worst-case approach with respect to severity and relationship to Study Treatment. All serious AEs will also be summarized as above.

The main summary of safety data will be based on events occurring within 14 days of any dose. For this summary, the frequency of preferred term events will be compared between study arms with risk differences and 95% confidence intervals, using the method of Miettinen and Nurminen [27]. As this analysis will use many event categories, and produce many confidence intervals, caution should be exercised when interpreting these confidence intervals. Separate summaries will be based on events occurring within 7 days of any dose and regardless of when they occurred.

Any AEs with a missing or partial onset date will be included in the overall AEs, but not be included within specified day-range summaries. AE duration will be calculated as (Stop Date – Start Date) + 1.

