Study Phase: 3

Primary Hypothesis: Three 6 mg doses of VGX-3100 (DNA Plasmids encoding E6 and E7 proteins of HPV-16 and HPV-18) delivered intramuscularly (IM) followed by electroporation (EP) with CELLECTRA[™] 5PSP to adult women with histologically confirmed HSIL[Cervical Intraepithelial Neoplasia (CIN)2, CIN3] of the cervix, associated with HPV-16 and/or HPV-18 will result in a higher percentage of women with histopathological regression of cervical HSIL lesions to no evidence of cervical HSIL and virologic clearance of HPV-16 and/or HPV-18 compared to placebo delivered IM followed by EP with CELLECTRA[™] 5PSP at the Week 36 visit²

Study Drug Dose	6 mg (1 ml)	
Administration Intramuscular injection followed by EP with the CELLECTRA™ 5P device		
Schedule	Schedule Day 0, Week 4, and Week 12 study visits	
No. of Subjects	Approximately 198 subjects will be randomized in a 2:1 ratio to receive VGX-3100 or placebo	
Study Duration 88 weeks		
Primary Objective Determine the efficacy of VGX-3100 compared with placebo with respect to combined histopathologic regression of cervical HSIL and virologic clearance of HPV-16 and/or HPV-18		
Primary Endpoint	Proportion of subjects with no evidence of cervical HSIL on histology (i.e. biopsy or excisional treatment) and no evidence of HPV-16 and/or HPV-18 in cervical samples by type specific HPV testing at Week 36 visit	

¹ Terminology based on 2012 consensus recommendation on Lower Anogenital Squamous Terminology (LAST) from the American Society of Colposcopy and Cervical Pathology (ASCCP) and the College of American Pathologists (CAP) ² The time frame is defined as any time starting from 14 days prior to the protocol-specified target date of Week 36

Secondary Objectives	Associated Secondary Endpoints
1. Evaluate the safety and tolerability of	la. Incidence and severity of local and systemic
VGX-3100 delivered IM followed by EP	events for 7 and 28 days following each
with CELLECTRA [™] 5PSP	investigational treatment and for the duration of
	the study (through Week 88 visit)
	1b. Incidence and severity of all adverse events
	including Serious adverse events (SAEs) (e.g.
	Suspected unexpected serious adverse reaction
	(SUSAR), Unexpected adverse device effect
	(UADE) and other unexpected AEs) for the
	duration of the study (through Week 88 visit)
2.Determine VGX-3100 efficacy compared	
to placebo as measured by histopathologic	cervical HSIL on histology (i.e. biopsies or

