7 EVALUATION OF SAFETY AND MANAGEMENT OF TOXICITY

7.1 SAFETY PARAMETERS

7.1.1 ADVERSE EVENTS

An adverse event (AE) is defined as any unfavorable and unintended change in the structure, function, or chemistry of the body, or worsening of a pre-existing condition, temporally associated with the use of a product whether or not considered related to the use of the product. In this study, such changes will be monitored, classified, and summarized, as Clinical or Laboratory AEs. Medical condition/diseases present before starting the investigational drug will be considered adverse events only if they worsen after starting study treatment. Throughout the course of the study, all solicited and unsolicited AEs will be monitored and reported on an AE CRF, including the event's seriousness, severity, action taken, and relationship to investigational product(s). AEs should be followed until resolution or stable and the outcome will be documented on the appropriate CRF. All AEs should be recorded in standard medical terminology rather than the subject's own words.

AEs include the following:

- Pre- or post-treatment complications that occur as a result of protocol mandated procedure during or after screening (before the administration of study drug).
- Any pre-existing condition that increases in severity, or changes in nature during or as a consequence of the study drug phase of a human clinical trial, will also be considered an AE.
- Complications of pregnancy (e.g., spontaneous abortion, miscarriage, ectopic pregnancy, fetal death, still birth, congenital anomaly of the fetus/newborn); see Section 7.1.9 for additional information on pregnancy reporting.
- AEs that occur from the study screening visit onwards and throughout the duration of the study, including the follow-up off study drug period will be recorded as an AE.
- Conditions that lead to a medical or surgical procedure.

AEs do not include the following:

- Medical or surgical procedures (e.g., surgery, endoscopy, tooth extraction, transfusion) performed as a result of an AE.
- Pre-existing diseases or conditions or laboratory abnormalities present or detected before the screening visit that do not worsen.
- Situations where an untoward medical occurrence has not occurred (e.g., hospitalization for elective surgery, social and/or convenience admissions).
- Overdose without clinical sequelae.

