7.1.9 PROCEDURES FOR DOCUMENTING PREGNANCY DURING STUDY

Subjects who are pregnant or expect to become pregnant during the course of the study up to Week 36 will be excluded from participation in the study. Should a subject become pregnant after receiving the first study treatment in the study, she will not be given any further study treatments. A Pregnancy Form will be completed by the site personnel and submitted to the sponsor or its designee within 24 hours after learning of the pregnancy. Site personnel will submit the Pregnancy Form to the Sponsor or its designee by fax, as described in Section 7.4.2.

The investigator will also report this event to the IRB within 24 hours of becoming aware of the pregnancy. Sites must request the subject's permission to query pregnancy outcome and follow each subject to determine the outcome of the pregnancy. Results will be summarized in the clinical study report (CSR).

Subjects who become pregnant at any point during the study will continue to be followed for safety assessments without receiving further study treatment. Procedures that are contraindicated during pregnancy, including additional treatments, must not be performed. Investigators should use clinical judgment regarding subsequent study-related blood collection based on the presence or absence of anemia in each subject.

All pregnancies that occur from the time of first study treatment through the follow up visits must be reported. The investigator will monitor the subject and follow the outcome of the pregnancy. If the end of the pregnancy occurs after the study has been completed, the outcome will be reported directly to the study team and the medical monitor.

7.2 METHODS AND TIMING OF THE COLLECTION AND RECORDING OF SAFETY DATA

Non-serious AEs and SAEs (and UADEs) will be collected for each subject from the time when informed consent is obtained through Week 88.

The sources of AEs cover:

- 1. The subject's response to questions about her health (a standard non-leading question such as 'How have you been feeling since your last visit?' is asked at each visit).
- 2. Symptoms spontaneously reported by the subject.
- 3. Evaluations and examinations where the findings are assessed by the investigator to be clinically significant changes or abnormalities.
- 4. Other information relating to the subject's health becoming known to the investigator (e.g. hospitalization).

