8.11.1 ADVERSE EVENTS

All AEs will be summarized among the safety population by frequency per treatment arm. These frequencies will be presented overall and separately by dose, and will depict overall, by system organ class and by preferred term, the percentage of subjects affected. Additional frequencies will be presented with respect to maximum severity and to strongest relationship to Study Treatment. Multiple occurrences of the same AE will be counted only once following a worst-case approach with respect to severity and relationship to Study Treatment. All serious AEs will also be summarized as above.

The main summary of safety data will be based on events occurring within 28 days of any dose. For this summary, the frequency of preferred term events will be compared between study arms with risk differences and 95% confidence intervals, using the method of Miettinen and Nurminen [29]. As this analysis will use many event categories, and produce many confidence intervals, caution should be exercised when interpreting these confidence intervals. Separate summaries will be based on events occurring within 7 days of any dose and regardless of when they occurred.

For AE data, partial start dates will be imputed to the date of treatment to conservatively report the event as treatment-emergent, whenever the portion of the date is consistent with that of the study treatment. Otherwise, it will be imputed to the earliest date consistent with the partial date. A completely missing onset date will be imputed as the day of treatment. Partial stop dates will be assumed to be the latest possible day consistent with the partial date.

AE duration will be calculated as (Stop Date – Start Date) + 1.

8.12 VITAL SIGNS

Measurements for vital signs as well as changes from baseline will be summarized with descriptive statistics: mean standard deviation, minimum, median, and maximum values by time point and treatment arm, for the Safety population. Baseline is defined as the last measurement prior to the first treatment administration.

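### Capturing each adverse event once at its maximum severity leaves no date for a worsening after a later dose, so the 7-day, 28-day and by-dose summaries can miss or misplace it

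*Protocol*

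**What the plan says.** All references are to protocol version 5.0. The sentence in Section 7.1.5 is identical in the earlier versions bound into the same file.

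- **Capture rule (7.1.5):** "Adverse events should be captured once on the CRF at the maximum severity reported".
- **Collection period (7.2):** "Non-serious AEs and SAEs (and UADEs) will be collected for each subject from the time when informed consent is obtained through Week 88". A record can therefore be open before Day 0.
- **Dosing (synopsis):** "Day 0, Week 4, and Week 12 study visits".
- **Main safety summary (8.11.1):** "The main summary of safety data will be based on events occurring within 28 days of any dose".
- **Other summaries (8.11.1):** "Separate summaries will be based on events occurring within 7 days of any dose and regardless of when they occurred". Frequencies are also shown by dose and by maximum severity, and repeat occurrences of the same event count once at the worst case.
- **Dating (8.11.1):** "partial start dates will be imputed to the date of treatment to conservatively report the event as treatment-emergent", where the known part of the date allows it. This is the only place where the section connects a date with treatment emergence.
- **Definition (7.1.1):** adverse events include "Any pre-existing condition that increases in severity, or changes in nature during or as a consequence of the study drug phase". The section also says that a condition present before the drug is started becomes an adverse event only if it worsens afterwards, that events from the screening visit onwards are recorded, and that a condition with onset before consent belongs in the medical history.

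**The concern.** Secondary endpoint 1a (Section 3.3) is the incidence and severity of local and systemic events in the 7 and 28 days after each treatment, and over the whole study. An event that was mild before a dose and becomes severe after it is one of the things these summaries should show. With one record per event, one start date and the worst grade ever reached, the record says how bad the event became but not when.

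This cannot be left to an analysis plan. It concerns what sites write down, and no later analysis can recover a date that was never collected.

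**Working it through.** There is no stated figure to reproduce. The check is day arithmetic plus a comparison of sections.

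**Inputs.** Doses at nominal Days 0, 28 and 84 (synopsis), with ±4 days for doses 2 and 3 (Table 1). Windows of 28 and 7 days (8.11.1). Assumption: each event is placed by its single recorded start date.

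**28-day windows, nominal.** Days 0-28, 28-56 and 84-112. Uncovered before dose 3: Days 57-83, which is 83 − 57 + 1 = 27 days.
- Doses at Days 24 and 88: windows end on Day 52 and restart on Day 88. Uncovered: Days 53-87 = 35 days.
- Doses at Days 32 and 80: uncovered are Days 29-31 (3) and 61-79 (19) = 22 days.

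**7-day windows, nominal.** Days 0-7, 28-35 and 84-91. Uncovered before dose 3: Days 8-27 (20) and 36-83 (48) = 68 of 84 days. With the same shifts: 16 + 56 = 72 of 88 days, and 24 + 40 = 64 of 80 days.

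**What happens to an event that worsens after the next dose (nominal dosing):**

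| Recorded start | 28-day any-dose summary | 7-day any-dose summary | By-dose table | Any-time summary |
|---|---|---|---|---|
| Days 0-7 or 28-35 | in, at worst grade | in, at worst grade | worse grade credited to the earlier dose | in, at worst grade |
| Days 8-27 or 36-56 | in, at worst grade | out | worse grade credited to the earlier dose | in, at worst grade |
| Days 57-83 | out | out | not shown under dose 3, where it worsened | in, at worst grade |
| Consent to before Day 0 | depends on which section is followed | same | same | in, at worst grade |

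**The last row.** A symptom that starts after consent and before Day 0 is already an adverse-event record, because events are recorded from screening. If it worsens after dose 1, Section 7.1.1 points to an adverse event arising at the worsening, whereas Section 7.1.5 says the event is captured once. Nothing in the protocol says which prevails, so two sites could record the same course differently.

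**A contrast within 8.11.1.** A completely missing onset date is imputed to the day of treatment, which favours counting the event as treatment-emergent. A documented worsening after a dose, with a known earlier onset, gets no such treatment.

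**The case against.** **The protocol does not say that a worsened event keeps its first onset date.** True; this is an inference. But one record per event with one start date leads there, and no section provides for a second record or a date of worsening.

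**A reader might infer that every worsening of a symptom that began between consent and Day 0 is lost.** The documents do not support that. Section 7.1.1 treats worsening after treatment starts as an adverse event, and Section 6.3.3.10 has diary entries that meet Grade 1 or higher documented as adverse events unless they belong to the ongoing medical history. What stands is an unreconciled conflict, not a certain loss.

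**A reader might also infer that the main 28-day comparison understates severity throughout.** That goes too far. At nominal dosing, onsets on Days 0-56 remain in the any-dose summary at their worst grade. The comparison between arms there is of preferred-term frequency, so moving an event between doses does not alter it. The any-time summary keeps everything.

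**Safety oversight does not depend on these windows.** Correct. The events of special interest (7.3.1) and the pausing rules (7.3.2) work on grade and relatedness.

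**Few events would still be open at the next dose.** Plausible. Section 2.3 describes the commonest Phase 2b events, administration-site reactions, as generally mild and limited to a few days.

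**One record at worst grade is an accepted convention.** It is, and it suits an overall table. It suits less well a plan that also reports by window and by dose.

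**Conclusion.** The point holds in a limited form. If Section 7.1.5 is followed as written and events are placed by start date, a worsening after a dose is missed by the 28-day summary for onsets on nominal Days 57-83 (27 days; 22 or 35 days in the two shifted schedules checked). It is missed by the 7-day summary for onsets on Days 8-27 and 36-83 (68 of the 84 days before dose 3). The by-dose severity table credits a later worsening to the earlier dose. For events starting between consent and Day 0, Sections 7.1.5 and 7.1.1 must be reconciled.

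The number of events affected cannot be computed. The documents give no rate of worsening, and applying a guessed percentage to the 594 planned dosings (198 × 3) would have no basis in them. The number is probably small. This is a cheap improvement, not an error that endangers the main safety conclusion.

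**What to change.** Amend Section 7.1.5 and the CRF completion guideline along these lines: *Each adverse event is recorded at its maximum severity. If an ongoing event increases in grade after a study treatment, a new record (or a dated grade change) is entered with the date of worsening; the earlier entry keeps the highest grade reached before that treatment. This applies also to events that began between consent and Day 0.* Add to Section 8.11.1 that the 7-day and 28-day windows and the by-dose tables use the date of worsening for such entries.

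Subjects are not double counted, because Section 8.11.1 already counts repeat occurrences of the same event once at the worst case. The cost is a few extra adverse-event entries and a line of site guidance, with no added visits. If new records are used instead of dated grade changes, they should be linked to the first record so that the duration formula in Section 8.11.1 can still be applied to the whole event.
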